7.4 Resource valorization

Direct medical and non-medical costs will be annualized, assuming consistent/representative resource use over the measurement period (months).

1. Non-reimbursable healthcare resources

- Weekly quantity valued at the average sale price;
- Quantity of other over-the-counter products (e.g., medical devices, oral nutritional supplements (ONS), etc.) valued at the average sale price;
- Number of hours of paramedical care valued at the corresponding wage/convention rate (if available);
- Quantity of technical equipment for disability compensation valued at the average sale price.

2. Medico-social resources

- Use of medico-social support: number of hours valued at the service rate, or, if unavailable, at the average hourly wage of equivalent professionals in France;
- Total costs of stays and consultations in medico-social facilities related to the specified medical condition within the medico-social sector.

3. Other non-medical resources

- Home adaptations: family expenses (lifetime);
- Modification of vehicles and/or purchase of an adapted vehicle: family expenses (lifetime);
- Non-medical transportation: weekly mileage valued according to the mileage reimbursement rate for personal vehicles.

4. Informal help

Care hours provided by caregivers valued at the cost of a replacement salary, according to the Proxy Good Method (PGM), and hours for activities of daily living valued at the average salary of a housekeeper.

5. Productivity loss

Lost work hours related to the DMD (Degenerative Motor Disorder) that do not pertain to caregiving, valued at the average hourly wage in France.

6. Assistance and allocations

Total monthly benefits related to DMD (Degenerative Motor Disorder) received by the patient and/or the family in the medico-social sphere.

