4.2 Assessment criteria

4.2.1 Main criterion

Average annualized cost per patient/family.

Table 2 below shows the typology of all the costs considered in this study.

Table 2: typology of all study costs.

		Postes de coûts recueillis dans le cadre de l'étude 'CouDuMyo'
Coûts directs	Coûts médicaux non remboursables	
 ▪ Médicaments en vente libre ▪ Autres produits de santé en vente libre (ex : petits dispositifs médicaux, compléments nutritionnels oraux...) ▪ Equipements techniques de compensation du handicap ▪ Consultations de professionnels paramédicaux non pris en charge par l'Assurance Maladie (ex : ergothérapeute ou psychologue en ville...)
	Coûts liés à la sphère médico-sociale	
 ▪ Auxiliaire de vie, éducateurs spécialisés, assistants sociaux, accompagnement à la scolarité ▪ Hébergement en établissement médico-social ▪ Consultations dans des services médico-sociaux
	Coûts non-médicaux	
 ▪ Adaptation du domicile, adaptation du véhicule ▪ Transports non médicaux ▪ Aide informelle pour les soins (aidant familial, bénévole, autre) ▪ Aide informelle pour les activités quotidiennes ▪ Recours à une aide hors secteur sanitaire pour les actes de la vie quotidienne (ménagère, auxiliaire de vie, etc.)
Coûts indirects	Coûts indirects pour le patient	
 ▪ Pertes de productivité (adulte) ▪ Perte de jours d'école (enfant)
	Coûts indirects pour les aidants	
Pertes de temps dédié :
 
 ▪ à une activité professionnelle (aidant travaillant), ▪ ou de loisir (aidant non travaillant), 
hors temps consacré aux soins².

Aides financières	Coûts liés aux allocations/aides financières	Dispositifs permettant de financer (hors budget de l'Assurance Maladie dans le cadre de l'ALD) tout ou partie des coûts identifiés (ex : allocation compensatrice pour personne tierce (ACTP), allocation adultes handicapés (AAH), allocation d'éducation de l'enfant handicapé (AEEH), prestations de compensation du handicap (PCH)...)

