7.2 Timeframe

The time horizon will be one year (retrospective) of patient care.

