7.3 Identification et quantification des ressources consommées

The resources consumed will be identified and quantified:

1. Non-reimbursable health resources

- Name and weekly quantity of OTC drugs consumed in a representative month;
- Name, type and quantity of other OTC products (e.g. small medical devices, oral nutritional supplements, etc.) purchased in a representative month;
- Number and type of paramedical consultations carried out in a representative month;
- Number and type of non-reimbursable technical equipment for disability compensation purchased since DMD diagnosis.

2. Ressources de la sphère médico-sociale

Medico-social costs include those incurred by the medico-social sector. This includes social and medico-social establishments and services (ESMS) and social action assistance.

There are two main types of establishment:

- Establishments and services for disabled adults;
- Establishments and services for disabled children and adolescents.

The following variables will be collected:

- Frequency, duration and type of stay in a social and medico-social institution in the last month;
- Number of visits to a medical-social service in the last month.

3. Support for schooling and Professional life

- Schooling programs;
- Socio-professional support services.

The following variables will be collected:

- Number and type of support staff (carers, special educators, social workers, etc.) in the last month;
- Type of schooling, specific assistance and how many hours, if not in which structure, and what additional costs in the last month;
- Working hours, support arrangements and how many hours over the past month.

4. Other non-medical resources

- Recours à une aide hors secteur sanitaire pour les actes de la vie quotidienne (ménagère, auxiliaire de vie, etc.), type et nombre d'heures hebdomadaires ;
- Aménagements réalisés au domicile, depuis le diagnostic ;
- Adaptation du(des) véhicule(s) et/ou acquisition d'un véhicule aménagé, depuis le diagnostic
- Modalité des transports non médicaux, fréquence et kilométrage hebdomadaire.

5. Informal help

- Number of caregivers over 18 years old in total, degree of kinship;
- Number of hours spent with the patient providing support for care, daily living activities, and instrumental activities of daily living.

6. Productivity loss

- For the primary caregiver: Changes in situation, absenteeism, and presenteeism related to DMD;

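### Section 7.4 gives no annualisation rule that fits equipment, home adaptations and vehicles: they are collected since diagnosis, but its one rule assumes steady use over months

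*Combined protocol and SAP*

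**What the plan says.** Section 4.2.1 defines the main criterion as "Average annualized cost per patient/family", and section 7.2 sets the window: "The time horizon will be one year (retrospective) of patient care".

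Section 7.3 records most recurrent resources per week or per month. Three groups have a different window. Equipment is recorded as "Number and type of non-reimbursable technical equipment for disability compensation purchased since DMD diagnosis". Home work is recorded as "Aménagements réalisés au domicile, depuis le diagnostic", and vehicle adaptation or purchase likewise since diagnosis.

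Section 7.4 values these groups as follows: "Quantity of technical equipment for disability compensation valued at the average sale price"; "Home adaptations: family expenses (lifetime"; "Modification of vehicles and/or purchase of an adapted vehicle: family expenses (lifetime". Its only statement on how direct costs become annual is "Direct medical and non-medical costs will be annualized, assuming consistent/representative resource use over the measurement period (months". No useful life, amortisation period or discount rate appears anywhere. Section 8.5 leaves a detailed SAP to be written before database freeze.

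On dates, neither chapter 7 nor the list in 6.3.2 mentions a purchase date or a diagnosis date. Section 6.3.2 refers to the appended questionnaire for cost variables, and that questionnaire was not available for this review. Section 9.1 puts age at diagnosis among the BNDMR sampling variables, and 12.2 says that the questionnaire data will not be matched to BNDMR data.

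**The concern.** A steady-use rule works for over-the-counter drugs or weekly mileage: observe a month, scale to a year. An adapted vehicle or a home conversion is bought once and used for years. Neither the sum spent since diagnosis nor a scaled version of it is the cost of one year's use, so the rule gives no valid annual figure for these items.

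Section 2.1 ranks disability aids and home and vehicle modifications among the largest cost categories in the literature. The open choice therefore reaches the main criterion and all three secondary criteria: cost by type, cost by severity stage and cost drivers. The severity comparison is the most exposed, because time since diagnosis, and with it accumulated purchases, tends to rise with severity. A bias of this kind does not shrink with more interviews and does not show in the confidence interval.

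**Working it through.** **1. The plan's own figure.** Section 8.1 gives a coefficient of variation of 1, a precision of 15% and 171 pairs. With a two-sided 95% interval (assumed; the level is not stated), n = (1.96 × 1 / 0.15)² = 170.7, rounded up to 171. The half-width at 171 is 1.96/√171 = 15.0%. This is the yardstick below.

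**2. One item under different rules.** Take EUR 10,000 of purchases (assumed amount). One reading of 7.4 treats the time since diagnosis as the measurement period, so annual cost = amount × 12 / months since diagnosis. The plan does not state this rule. The window runs from just over 6 months (5.1) to decades (2.1 notes survival beyond 40). Seven months and 20 years are taken as examples. The alternative is an equivalent annual cost, amount × r / (1 − (1+r)^−L), or amount / L when r = 0, with useful life L and discount rate r both assumed.

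| Rule | EUR per year |
|---|---|
| Divided by time since diagnosis, 7 months (12/7 = 1.71) | 17,143 |
| Divided by time since diagnosis, 20 years (12/240 = 0.05) | 500 |
| Equivalent annual cost, L = 5, r = 0% to 4% | 2,000 to 2,246 |
| Equivalent annual cost, L = 15, r = 0% to 4% | 667 to 899 |

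Under division, the same item differs 34-fold between the two patients. The equivalent annual cost does not depend on time since diagnosis. The contrast holds one item fixed. A patient at 20 years will usually have bought more items, so this is not the distortion of a patient's total.

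**3. Illustration on the mean and the severity ratio, under the same reading.** Inputs are the Portuguese row of Table 1, in EUR. D is non-medical minus informal care; T is non-medical plus indirect.

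- Ambulatory: D = 11,890 − 9,996 = 1,894; T = 11,890 + 4,395 = 16,285.
- Non-ambulatory: D = 29,717 − 20,772 = 8,945; T = 29,717 + 10,211 = 39,928.
- Ratio of T: 39,928 / 16,285 = 2.45.

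Components are used because the two printed totals appear exchanged. The non-ambulatory total (19,993) is below its own components. With the totals swapped, informal care is 9,996/19,993 = 50.0% and 20,772/48,991 = 42.4%, which agrees with the 42% to 50% in section 2.1.

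Let s be the durable share of D, f the fraction of time since diagnosis spent non-ambulatory, and p the non-ambulatory share of the sample. All three are assumed. Suppose durable cost accrues at s × 1,894 a year before loss of ambulation and s × 8,945 after. Division by time since diagnosis then gives a non-ambulatory patient s × [f × 8,945 + (1 − f) × 1,894]. The shortfall is s × (1 − f) × 7,051.

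| s, f, p | Non-ambulatory total | Severity ratio | Overall mean |
|---|---|---|---|
| 0.20, 0.7, 0.4 | −1.1% | 2.43 | −0.7% |
| 0.50, 0.5, 0.5 | −4.4% | 2.34 | −3.1% |
| 0.75, 0.3, 0.6 | −9.3% | 2.22 | −7.3% |
| 1.00, 0.3, 0.6 | −12.4% | 2.15 | −9.7% |

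For the third row: shortfall 0.75 × 0.7 × 7,051 = 3,702; 3,702/39,928 = 9.3%; mean T = 0.6 × 39,928 + 0.4 × 16,285 = 30,471; 0.6 × 3,702/30,471 = 7.3%.

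The non-ambulatory durable line itself falls by (1 − f) × 7,051/8,945, which is 24% at f = 0.7 and 55% at f = 0.3.

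These figures are not bounds. The model gives ambulatory patients no bias by construction, whereas step 2 shows that recently diagnosed patients can be overcounted, so the net sign is open. D is also a rough proxy: Table 2 places equipment under medical costs, and non-medical costs include transport and paid help.

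**The case against.** The strongest reply is that this is missing detail and not an error. The SAP due under 8.5 can set useful lives, discount rate and price year. Division by time since diagnosis is an inferred rule. In a text that reads as a translation, the word lifetime could even mean an item's service life. The size is modest as well: the whole of D is 1,894/16,285 = 12% of the ambulatory sum and 8,945/39,928 = 22% of the non-ambulatory sum.

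Much of this stands. It does not remove the point, because the one rule that 7.4 does state covers all direct costs and does not fit durables. If lifetime means service life, no length is given. A SAP can choose a useful life, but it cannot supply a purchase year that nobody asked for. Section 8.4 allows follow-up of consenting families when answers are missing, and centres keep their correspondence tables until freeze (12.2). Late recontact is therefore possible in principle, but it would mean a second call.

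Three stronger readings go beyond the documents:

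- A reader might infer that cumulative sums enter the annual cost undivided. Section 7.4 says that direct costs will be annualised.
- A reader might infer from 9.1 and 12.2 that age at diagnosis will be unavailable to the analysis. The appended questionnaire may ask for it, and the list in 6.3.2 concerns representativeness and adjustment, so absence there is weak evidence.
- A reader might infer that all durables need past prices brought to one year. Equipment is valued at an average sale price; only home and vehicle expenses raise that issue.

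**Conclusion.** The point holds, and it should be fixed before questionnaires are sent. For equipment, home adaptations and vehicles, the plan combines a since-diagnosis window with a rule for steady monthly use. It states nothing that would turn the purchases into a one-year cost.

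The size cannot be derived from the documents. On assumed values of s, f and p, and only under division by time since diagnosis, the overall mean is 0.7% to 7.3% too low (9.7% if all of D is durable). That is inside the 15% precision target. The larger effects are on the non-ambulatory durable line and on the severity ratio, which falls from 2.45 to between 2.22 and 2.43 in the first three scenarios. Confidence is moderate, because the questionnaire may already hold the dates. The missing rule in 7.4 stands either way.

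**What to change.** 1. In 7.4, restrict the monthly rule to recurrent items.
2. For durables in use during the 12-month window, compute an equivalent annual cost with a stated useful life per item type and a stated discount rate. Put home and vehicle family expenses in one price year.
3. Before questionnaires are sent, confirm that the questionnaire records the purchase year of each durable item and whether it is still in use, or add these two fields.
4. Add one sensitivity analysis that varies the useful lives.

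The cost is wording in 7.4 and the SAP, plus at most two fields per durable item. If the fields already exist, only wording changes. The sample size is unaffected. The downsides are a slightly longer interview (the maximum is 30 minutes in 6.3.2 and 60 in 6.1), recall error on purchase year, and reliance on assumed useful lives, which item 4 makes visible.

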2 SCIENTIFIC RATIONALE

2.1 Current state of knowledge

Background to the study

Duchenne muscular dystrophy (DMD) is a chronic neuromuscular disease affecting around 150 to 200 newborns per year, characterized by progressive muscle atrophy and weakness caused by complete dystrophin deficiency. DMD has a severe phenotype, with death most often occurring in the 3rd decade.

Muscular weakness begins with damage to the lower limbs, then the back and upper limbs, leading to progressive loss of the ability to walk, which occurs on average in early adolescence. As the disease progresses, damage to the respiratory, cardiac and digestive muscles leads to other disorders affecting the patient's life. Other disturbances may also be observed, such as emotional disorders, learning difficulties or episodes of anxiety and depression. Relatives (or informal caregivers) are therefore heavily involved in the day-to-day management of the consequences of the pathology.

Patients are currently cared for within the Filnemus rare disease network, via reference and competence centers. Treatment (based on daily corticosteroids, cardioprotective drugs, regular physiotherapy, respiratory physiotherapy and spinal arthrodesis¹) has improved life expectancy over time. Over 90% of children with DMD now reach adulthood, and some now live beyond the age of 40¹. New treatments, such as gene therapies, are currently in clinical development for this disease, with a major potential impact on current management and the organization of care.

Very little data is available on the use of care and associated costs for DMD patients, particularly in the context of care in France. The AP-HP has proposed a protocol to study the care pathway of these patients, using data from the Banque nationale des données maladies rares (BNDMR) and the Système national des données de santé (SNDS). It will be used to describe patient characteristics, healthcare utilization and associated costs. With regard to the latter, only direct costs eligible for reimbursement (Affection Longue Durée 100%) can be analyzed.

However, other resources are consumed by DMD patients, notably for their medical care, and are not eligible for reimbursement. What's more, the patient's level of dependence may mean that he or she has to make adjustments or incur other expenses outside the health sphere, but linked to the pathology. Finally, informal help can be very important. All these family costs need to be estimated.

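### Section 7.4 values the purchase of an adapted vehicle without deducting the ordinary car the family would have owned anyway, so read literally it charges non-disease cost to DMD

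*Combined protocol and SAP*

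**What the plan says.** Three places describe the vehicle item, and they differ in scope.

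- Table 2 (section 4.2.1), introduced as the typology of all costs in the study, lists under non-medical costs "Adaptation du domicile, adaptation du véhicule". Buying a vehicle does not appear.
- Section 7.3, item 4, collects "Adaptation du(des) véhicule(s) et/ou acquisition d'un véhicule aménagé, depuis le diagnostic". Acquisition has now been added.
- Section 7.4, item 3, values it as "Modification of vehicles and/or purchase of an adapted vehicle: family expenses (lifetime"). Modification and purchase are pooled, and nothing is deducted.

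A separate line in the same item of section 7.4 covers travel: "Non-medical transportation: weekly mileage valued according to the mileage reimbursement rate for personal vehicles". The data behind it are "Modalité des transports non médicaux, fréquence et kilométrage hebdomadaire" (section 7.3, item 4). The rate, its source and its components are not given.

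On attribution, section 2.1 explains that families may have to "incur other expenses outside the health sphere, but linked to the pathology". On annualisation, section 7.4 opens with "Direct medical and non-medical costs will be annualized, assuming consistent/representative resource use over the measurement period (months"). No useful life or residual value is given for a purchase made once.

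**The concern.** A vehicle bought already adapted is partly a car and partly an adaptation. Most families would have had some car without the disease, so only the second part is a cost of DMD. The survey is non-comparative (section 4.1), so no control group removes ordinary car ownership. The valuation rule is the only place where that can happen, and as written it does not.

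The item enters the main criterion (average annualised cost per patient or family), the cost by type, and the cost by severity stage. Section 8.3 adds analyses by mobility. Families of non-ambulatory patients are the more likely buyers, so an excess here would probably fall unevenly across the groups being described to HAS and CEPS.

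A second question is whether the mileage line charges part of the same vehicle again. The plan guards against double counting elsewhere: a footnote to Table 2 keeps care time out of caregivers' indirect costs. Vehicles have no such guard.

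**Working it through.** **The plan's own figures.** The documents give no vehicle price, adaptation share, period of use, mileage or rate, so there is no vehicle figure to reproduce. The sample size in section 8.1 does reproduce: n = (1.96 × 1 / 0.15)² = 170.7, rounded up to 171, with the stated coefficient of variation of 1, the stated precision of 15% and an assumed two-sided 95% level. It does not depend on this point. Equally, a larger sample would not remove an excess built into the valuation rule.

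**Ordinary-car part.** Let P be the purchase price, A the adaptation part and L the years of use.

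- Literal rule, per year: P / L
- Incremental rule, per year: A / L
- Excess: (P − A) / L

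With assumed P = EUR 40,000, A = EUR 15,000 and L = 8:

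- 40,000 / 8 = EUR 5,000
- 15,000 / 8 = EUR 1,875
- Excess = 5,000 − 1,875 = EUR 3,125 per purchasing family per year

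Over a wider assumed range (P from EUR 30,000 to 60,000, ordinary-car share from 0 to 75%, L from 5 to 10 years) the excess runs from EUR 0 to 60,000 × 0.75 / 5 = EUR 9,000. Zero applies if only the extra cost is in fact recorded.

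**Effect on a mean.** If a share s of families bought such a vehicle, the mean rises by s × 3,125. For an assumed s of 10% to 50%, that is EUR 312.50 to EUR 1,562.50. For scale, Table 1 gives the Portuguese study's non-medical cost without informal care as 29,717 − 20,772 = EUR 8,945 for non-ambulatory patients and 11,890 − 9,996 = EUR 1,894 for ambulatory patients. Against EUR 8,945, the shift in the mean would be about 3.5% to 17.5%. The EUR 3,125 itself should not be set against that mean, because it applies to purchasers only.

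**Possible overlap with mileage.** Let k be weekly kilometres driven in the purchased vehicle, r the rate per kilometre and c the share of r that stands for ownership. The capital charged again is 52 × k × r × c per year.

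- c = 0 (rate covers running cost only): EUR 0
- Assumed k = 100, r = 0.40, c = 0.30: 52 × 100 × 0.40 × 0.30 = EUR 624
- Assumed k = 300, r = 0.60, c = 0.50: 52 × 300 × 0.60 × 0.50 = EUR 4,680

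This must not be added to the EUR 3,125. A rate for personal vehicles would recover ordinary-car capital at most, which is the same money. The sum 3,125 + 4,680 = EUR 7,805 would exceed the whole EUR 5,000 annual cost of the vehicle in the example.

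**Incremental pricing and overlap.** The cost becomes A / L + 52 × k × r. Ordinary-car capital has left the first term, so any that remains sits only in the mileage term. It is then counted once at most, whatever c is.

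**The case against.** The strongest reply is that the text does not force the literal reading. Section 7.4 speaks of what the family spent, which could mean the amount left after financial aid, or only the extra cost. Table 2 and section 2.1 both favour the narrower sense. The appended questionnaire, which would show what is asked, is not in the text available for review, so a field for the adaptation part may already exist. Section 8.5 also promises a detailed analysis plan before database freeze. This stands as a reason for moderation. It does not remove the point: the valuation rule names purchase, Table 2 does not, and no rule in the plan isolates the increment.

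A reader might go further and infer that vehicle capital is definitely counted twice. The documents do not support that. They never say what the mileage rate covers, and with a running-cost rate the overlap is nil. Nor do they say that all household driving is counted or that the kilometres are driven in the purchased vehicle. Any overlap is limited to purchasing families and their kilometres in that vehicle. Families that only modified a car show no evident overlap.

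A further objection concerns remedy. Using a running-cost rate for adapted vehicles and the full mileage rate for all others would, if the rate includes ownership, leave ordinary-car ownership charged to some families and not to others. That objection is right, and the split rate is not proposed here.

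**Conclusion.** The point holds as a cheap improvement. Read literally, section 7.4, item 3, attributes the ordinary-car part of an adapted vehicle to DMD. That goes beyond the cost list in Table 2 and the stated target of disease-linked expenses, and it overstates non-medical cost for purchasing families.

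The EUR 3,125 per purchasing family per year rests wholly on assumed price, adaptation part and years of use. The 8 years is an assumption because the plan has no rule for spreading one-off purchases; that gap affects the size of the excess, not its direction. The effect on the overall mean and on the comparison by mobility depends on the share of purchasers, overall and in each group, which the documents do not give. It is plausible that the mobility contrast is affected, but the documents do not show that it is materially inflated. Overlap with mileage remains conditional on what the rate covers.

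**What to change.** In section 7.4, item 3:

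1. Count only the adaptation cost. For a vehicle bought already adapted, count its price minus that of a comparable standard vehicle, with the reference price stated as an assumption.
2. Apply one mileage rate to all families and state what it covers. With incremental vehicle pricing, no separate running-cost rate is needed to avoid double counting.
3. State the period over which a vehicle expense is annualised, so that the increment can be turned into a yearly figure.

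Bring section 7.3, item 4, and Table 2 into line with this wording, and make sure the questionnaire records the adaptation part of the price.

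The cost is a few lines of text, possibly one questionnaire field, and a reference price that is itself an assumption and could be varied in a sensitivity analysis. The field should be settled before interviews begin: each family is interviewed once, and section 12.2 deletes the centres' correspondence tables at database freeze, so a missing split would be hard to recover. The comprehension check planned in section 6.3.2 is a natural place to try it.
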